Title	Randomized Pilot Crossover Study Comparing Virtual Reality (VR) and Non-VR Distraction for Decreasing Preoperative/Procedural Anxiety as a Function of the modified Yale Preoperative Anxiety Scale (mYPAS)
Short Title	VR-mYPAS study
Protocol Number	STU-2020-0607
Phase	Pilot
Methodology	Cross Over Design
Study Duration	Up to two years
Study Center(s)	Single-center – Children's medical center, Dallas, Texas
Objectives	To use the modified Yale Preoperative Anxiety Scale (mYPAS) to evaluate children prior to and during Port access, to look for a decrease preoperative anxiety during distraction in pediatric oncology patients undergoing port access.
Number of Subjects	77 patients
Diagnosis and Main Inclusion Criteria	CCBD patients requiring port access twice within a year
Study Product(s), Dose, Route, Regimen	mYPAS scoring while playing VR device versus non-VR distraction for Port access
Duration of administration	~ 15 minutes maximum (observation and completion of questionnaires after 10-minute familiarization with distraction method, during port access)
Reference therapy	N/A
Statistical Methodology	Cross over study will be performed. Subjects will be randomized (1 to 1 randomization via Proc Plan in SAS 9.4) at their initial encounter to either VR or Non-VR. During their second visit patients will be given the alternative mode of care (i.e. patients who initially received VR distraction will be given Non-VR distraction, and patients who initially received Non-VR distraction will receive VR distraction)

1.0 BACKGROUND AND RATIONALE

1.1 Disease Background

Pre-operative anxiety is common in children, with 50-70% of children experiencing it on the day of procedure (1). Children undergoing cancer treatment need multiple procedures throughout their course of treatment. Preprocedural anxiety can be particularly high in this group as the disruption to daily life, physical appearance, and the nature of therapy to include procedures, is aggressive to preserve health and life.

1.2 Study Agent(s)/Therapy(ies) Background and Associated Known Toxicities

The mYPAS observational scale will be used to assess VR and non-VR distraction for decreasing preoperative/procedural anxiety in pediatric oncology patients undergoing port access. It is an observational scale that consists of five domains (activity, emotional expressivity, state of arousal, vocalization and use of parents) and has shown good to excellent inter-observer reliability (2). It can be applied to children two years and older although it was validated for use in the 5-12 age group (2).

VR technology can be used as a distractor to decrease preoperative/procedural anxiety in pediatric oncology patients undergoing port access. Side effects of VR technology are minimal but include motion sickness and nausea.

1.3 Other Agents

Child Life guided activities for pre- and intraprocedural distraction for anxiety management.

1.4 Rationale

The purpose of the research study is to evaluate the use of VR as a distractor to decrease preoperative/procedural anxiety in pediatric oncology patients undergoing port access. In a study looking at the use of VR for needle-related procedural pain and distress in children and adolescents in a pediatric oncology unit, while the quantitative data did not show reduction of pain and distress in the VR group, results from observational pain scores showed a decrease, and the interviews indicated that using VR could be a positive experience (3). In a study of pediatric burn patients, another population that requires repeated procedures, the patients randomized to the VR group had significantly lower pain and anxiety scores as well as achieved faster healing rates (4).

Most of the studies on VR used pain assessment scales like faces pain scale, visual analogue scale and FLACC focusing on its effect on pain rather than anxiety (3-6). There have been few studies examining the use of VR as a tool to decrease preoperative/procedural anxiety and even fewer studies utilizing the

mYPAS to assess the effect of VR on preoperative anxiety in children. The mYPAS is now considered the gold standard in assessing preoperative anxiety in children (1,2)

VR can be a safe, non-pharmacologic way, of decreasing preoperative anxiety with minimal side effects, improving quality of care, patient experience and satisfaction. CHST currently uses the Kind VR device in house as a method of procedural distraction in various locations. Kind VR is a research-based company that has partnered with several research hospitals in the United States and Canada. Areas of research where the kind VR device has been used includes vaso-occlusive crisis in children with sickle cell disease, pediatric cancer patients needing port access procedures, Emergency Room patients needing IV placement or laceration repair and in children needing surgical procedures to help with preoperative stress.⁷ A study of Virtual reality on children with sickle cell disease vaso-occlusive crisis concluded that The Kind VR Aqua software was able to provide distraction through total immersion.⁸ Another study using Kind VR was able to demonstrate the safety of VR interventions in children and adolescents with cancer undergoing port access procedure.⁵ CHST and this research group are not partnering entities with the Kind VR, and the Kind VR device is not being studied. The effect of virtual reality (VR) on preprocedural anxiety as measured by questionnaires and the observations of the modified Yale Preoperative Anxiety Scale (mYPAS) is being studied.

If VR proves clinically useful in decreasing pre-op anxiety, patients may potentially allow clinicians to treat them for any number of ailments using interactive VR in lieu of, or at decreased requirement for, medicinal anxiolysis or anesthesia. Avoiding and minimizing sedation can potentially decrease length of post anesthesia recovery room stay. In addition, physical therapy is a big part of rehabilitation for pediatric pain patients. By distracting patients from pain and anxiety, VR can help patients improve function and range of motion during physical therapy, decreasing days away from school and promoting return to normal activities faster. Looking at post anesthesia recovery room length of stay with and without VR and range of motion/outcome of physical therapy with and without VR are areas of potential further studies.

2.0 STUDY OBJECTIVES

2.1 Primary Objectives

- 2.1.1 To utilize the modified Yale Preoperative Anxiety Scale (mYPAS), a validated preoperative/procedural anxiety score, to decrease preoperative anxiety via distraction in pediatric oncology patients (primary outcome).

2.2 Secondary Objectives

2.2.1 Parents or legally authorized representative (LAR) subjective report decreased anxiety with the use of VR (secondary outcome).

2.3 Endpoints

2.3.1 We expect to see statistically significant changes in the preoperative anxiety scores using the mYPAS when the VR group is compared to the non-VR group.

2.3.2 We expect parents or the legally authorized representative (LAR) to subjectively report decreased anxiety with the use of VR.

3.0 SUBJECT ELIGIBILITY

Eligibility waivers are not permitted. Subjects must meet all the inclusion and exclusion criteria to be registered to the study. Study treatment may not begin until a subject is registered.

3.1 Inclusion Criteria

3.1.1 Any patient of the Children's Medical Center CCBD

3.1.2 5-18 years of age

3.1.3 Patient requiring their port accessed twice or more within a year

3.1.4 Ability to understand and the willingness to sign a written informed consent.

3.2 Exclusion Criteria

3.2.1 Subjects younger than 5 and older than 18

3.2.2 Patients requiring recovery in PICU or sites other than PACU

3.2.3 If parents or subject is not willing to participate

3.2.4 Subjects with severe developmental delays and subjects with developmental challenges preventing them from keeping the VR device on are also excluded

3.2.5 Patients who will not be in CCBD for port access at least twice within a year

4.0 STUDY PROCEDURES

4.1 Screening/Baseline Procedures

Potential subjects will be identified from the CCBD schedule. Subjects are not patients of the study investigator, so a member of the study staff will request permission from the treating team to approach and include subjects in the study.

The legal authorization of parents to be approached will be verified by a member of the study team before approaching them in the preoperative holding area.

The study will be explained to the subject (if old enough to participate in discussion) and the parents on a telephone call the night before the CCBD visit in order to determine interest in participation.. It will be explained that participation is completely voluntary and that whether they choose to participate or not will not affect their treatment in our facility. They will be given ample time to consider participation and ask any questions they may have with the study doctor and their treating physician. The next day, in clinic, it will be verified if they are still interested in participating, all questions will be answered by a member of the research team in the room virtually on the CHST telemedicine tablet platform. If they agree, written informed consent will be obtained and a copy of the signed consent form will be given to the subject's LAR by their nurse or child life specialist.

Children's Medical Center has a large Hispanic population; therefore, the study will be discussed using a certified on-site Spanish translator, or virtual platform Spanish translator if this language barrier exists. A Spanish version of the parent questionnaires and the consent form will be provided.

4.2 Procedures During Treatment

Once it is confirmed that the subject qualifies and the parents (LARs) are willing to participate, the parents (LARs) will be given the demographics form to fill out and the subject will be randomized in the study system. Whether the patient participates in the Virtual Reality group or the Non-Virtual Reality group first will depend on a computerized randomization process independent of the study researchers.

For the Non-virtual reality group, a member of the study team will evaluate the patient using the mYPAS prior to port access. Parents will be asked to fill out a questionnaire evaluating their child's preoperative anxiety after port access is complete (see study schema).

For the port access with virtual reality (VR) distraction, the patient will be able to play the VR game for 15 minutes prior to actual port access procedure start. During this first 5-15 minutes of being in their CCBD procedure/infusion room with the placement of the VR headset, a researcher will be doing the first mYPAS observation and scoring (Holding). The patient will then continue to play the game through the port access procedure. The point where the port access kit is opened by the nurse marks the start of the Port access portion of the mYPAS observation (Induction 1). The end of the second mYPAS observation is when the Tegaderm dressing is applied to the port access needle.

After port access is complete with VR, or control, the parents or LAR will then be asked to fill out a questionnaire assessing their child's perioperative anxiety.

NOTE: For safety of the researchers and patients, all mYPAS patient observations on day of CCBD visit, as well as any further consent questions, will be performed through a virtual telemedicine platform with approved tablets run and vetted by telemedicine at Children's Health System of Texas (CHST). The process has already been approved and vetted by CHST telemedicine so that there is little to no risk of virtual PHI breach. The observation of the patients will be done in real time with no recording of the encounter. Tablets are currently in place from CHST, and nursing and Child Life are informed of process.

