4.3 Follow-up Procedures

We will examine the CCBD schedule for the second opportunity to include each subject and complete the study in the other study arm (VR-distraction or Non-VR distraction). Surveys and Assessments will be filled out twice: once without the use of VR (control group) and the second time with the use of VR (study group).

Randomized Pilot Crossover Study Comparing Virtual Reality (VR) and Non-VR Distraction for Decreasing Preoperative/Procedural Anxiety as a Function of the modified Yale Preoperative Anxiety Scale (mYPAS)

Data collected will be compared and analyzed for statistically significant difference in anxiety scores with mYPAS. Parents' questionnaires will also be scored and evaluated for subjective improvement in parental assessment of preoperative anxiety.

All the study forms and questionnaires will be identified with the unique study ID number assigned in the study system with no other identifying data. There are no additional procedures outside the standard of care participants would normally receive. There will be no additional costs to subjects for participating in this study.

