8.5 Adherence to the Protocol

Except for an emergency situation, in which proper care for the protection, safety, and well-being of the study subject requires alternative treatment, the study shall be conducted exactly as described in the approved protocol.

8.5.1 **Exceptions** (also called single-subject exceptions or single-subject waivers): include any departure from IRB-approved research that is *not due to an emergency* and is:

- intentional on part of the investigator; or
- in the investigator's control; or
- not intended as a systemic change (e.g., single-subject exceptions to eligibility [inclusion/exclusion] criteria)

Reporting requirement: Exceptions are non-emergency deviations that require **prospective** IRB approval before being implemented. Call the IRB if your request is urgent. If IRB approval is not obtained beforehand, this constitutes a major deviation.

8.5.2 **Emergency Deviations:** include any departure from IRB-approved research that is necessary to:

- Avoid immediate apparent harm, or
- Protect the life or physical well-being of subjects or others

Reporting requirement: Emergency deviations must be promptly reported to the IRB within 5 working days of occurrence.

8.5.3 **Major Deviations** (also called **violations**): include any departure from IRB-approved research that:

- Harmed or placed subject(s) or others at risk of harm (i.e., did or has the potential to negatively affect the safety, rights, or welfare of subjects or others), or
- Affect data quality (e.g., the completeness, accuracy, reliability, or validity of the data) or the science of the research (e.g., the primary outcome/endpoint of the study)

Reporting requirement: Major deviations must be promptly reported to the IRB within 5 working days of PI awareness.

8.5.4 **Minor Deviations:** include any departure from IRB-approved research that:

- Did not harm or place subject(s) or others at risk of harm (i.e., did not or did not have the potential to negatively affect the safety, rights, or welfare of subjects or others), or
- Did not affect data quality (e.g., the completeness, accuracy, reliability, or validity of the data) or the science of the research (e.g., the primary outcome/endpoint of the study)

Reporting requirement: Minor deviations should be tracked and summarized in the progress report at the next IRB continuing review.

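### Section 4.2 describes during-access mYPAS scoring only for the VR visit, at odds with the Summary, and no visible passage names the score to be tested

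*Combined protocol and SAP*

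**What the plan says.** **VR visit (section 4.2).** There are two observations. Holding is scored in the first 5-15 minutes in the room with the headset on. For Induction 1, "The point where the port access kit is opened by the nurse marks the start of the Port access portion of the mYPAS observation", and the observation ends when the Tegaderm dressing goes on.

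**Non-VR visit (section 4.2).** There is one sentence: "For the Non-virtual reality group, a member of the study team will evaluate the patient using the mYPAS prior to port access". It gives no start mark, end mark or label, and describes no scoring during access. The sentence in 4.2 that covers both conditions concerns the parent questionnaire only.

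**Study Summary.** The Objectives row plans "to evaluate children prior to and during Port access" without limiting this to one arm. The Duration row has "observation and completion of questionnaires after 10-minute familiarization with distraction method, during port access", which also names no arm.

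**Section 4.3.** Assessments are completed once under each condition. It does not say how many mYPAS scores that means or over which windows.

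**Recording (section 4.2).** "The observation of the patients will be done in real time with no recording of the encounter".

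**Tested score.** Section 2.1 calls the mYPAS "a validated preoperative/procedural anxiety score, to decrease preoperative anxiety via distraction". Sections 2.3, 7.2, 7.3 and 7.4 refer to the mYPAS score, to preoperative anxiety, or simply to the difference between VR and non-VR. None names an observation window or a summary of the two.

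**The concern.** A crossover compares each child with himself or herself, so it needs the same measurement, taken at the same point of the visit, under both conditions. As written, 4.2 provides this at best for the waiting period. The title covers procedural as well as preoperative anxiety, and the Summary includes the access itself. If the observer follows 4.2, the procedural part of the question has no control measurement. Because scoring is live, the gap cannot be filled afterwards.

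The second issue follows from the first. The VR visit produces two scores, but the 3.5-point difference, the SD of 10, the paired test or mixed model, and the boundaries in Table 1 all presuppose one score per visit. Until that score is named, it could be chosen after data have been seen, including at the n=52 look.

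**Working it through.** **1. What the stated N presupposes.** Inputs from 7.2 and 7.4: difference 3.5, SD 10, power 0.80, attrition 10%, two-sided alpha 0.05. The SD is taken as that of the within-child difference, which the plan does not state.
- Normal approximation: n = [10 × (1.96 + 0.84) / 3.5]² ≈ 64, taken as 65 after rounding up the unrounded value. Then 65/0.90 = 72.2, so 73.
- Noncentral t: n = 67, and 67/0.90 = 74.4, so 75.
- Normal n with a 5% rank-test allowance: 65 × 1.05 = 68.25, so 69. Then 69/0.90 = 76.7, so 77.

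The stated 77 is therefore consistent with one paired comparison of one score per visit. The calculation is not in error. It does not say which score it is for.

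**2. Scores collected under each reading.**

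| Reading | VR | Non-VR | Per child | 77 enrolled | About 69 completers (77 × 0.90) |
|---|---|---|---|---|---|
| 4.2 as written | 2 | 1 | 3 | 231 | 207 |
| Both windows at both visits | 2 | 2 | 4 | 308 | 276 |

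The shortfall on the first reading is the whole set of non-VR during-access scores: 77 of 77 at enrolment, or 69 of 69 completers. On the second reading it is zero.

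**3. Comparisons each reading allows.**
- *4.2 as written:* VR Holding against non-VR pre-access is the only like-for-like pair, provided the unmarked control evaluation is taken at a comparable time. Induction 1 has no counterpart.
- *Both windows at both visits:* two matched pairs are available, and the plan does not say which is primary.

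**4. Does the analysis section settle the choice?** The mixed model in 7.3 has treatment, sequence and period as fixed effects and no term for observation window. The paired test takes one value per child per condition. Section 7.4 standardizes an effect in preoperative anxiety. None of these identifies a window.

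**5. Size of the open choice, as an illustration.** Suppose both windows are scored at both visits and each is tested at two-sided 0.05. The chance of at least one false positive is 1 − 0.95² = 0.0975 if the two tests are independent, 0.091 at correlation 0.5 and 0.070 at correlation 0.9. The correlations are assumed, the figures are for a single look, and the plan does not propose testing both. They show what naming one score in advance avoids.

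**The case against.** **The omission may be only apparent.** Section 4.2 cites a study schema, and the datasheet (10.4) is present only as a heading. Either may show both windows at both visits. The Summary's arm-neutral rows point the same way, so the short control sentence may be a drafting omission. This stands: it cannot be said that the trial lacks control during-access scores, only that 4.2 as written does not call for them and disagrees with the Summary.

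**Section 8.5 does not decide which text governs.** A reader might infer that, because "the study shall be conducted exactly as described in the approved protocol", the sentence in 4.2 must prevail. But the approved protocol includes the Summary and the schema too. The rule makes the contradiction matter; it does not resolve it.

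**A reader might infer a biased VR effect.** If VR Induction 1 were compared with a non-VR pre-access score, a rise in anxiety from waiting to access would be confounded with treatment. With a true effect of −3.5 and an assumed rise of 1.75 or 3.5 points, the expected difference would be −1.75 or 0. No passage proposes that unmatched comparison, and the documents give no figure for the rise. The matched pair under 4.2 as written carries no such bias if the control evaluation is taken at a time comparable to Holding. The bias is not part of this point.

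**The wording leans towards pre-access.** Sections 2.1, 2.3 and 7.4 speak of preoperative anxiety; in 2.1 the term preoperative/procedural describes the scale. That narrows the ambiguity without defining an endpoint, and the title names both. Taken alone, the unnamed score would be closer to missing detail. It weighs more here because the two visits are also described differently.

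**Conclusion.** The point holds as a contradiction between the Summary and section 4.2 on mYPAS scoring at the non-VR visit, together with a tested score that no visible passage names.

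Its size depends on which text staff follow. Under 4.2 as written, every non-VR during-access score is absent and unrecoverable, so the procedural comparison cannot be made; the pre-access comparison remains possible. If the schema or datasheet already sets both windows at both visits, nothing is lost and only the text of 4.2 has to be aligned. On either reading, the 3.5-point difference, the analysis and the Table 1 boundaries still have to be tied to one score, unless an unseen page already does so.

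The documents do not support a claim that the trial's estimate is biased or that N=77 is wrong.

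**What to change.** **Section 4.2.** Score the same windows with the same start and end marks at both visits: a pre-access window, and a during-access window from kit opening to Tegaderm. Make the text agree with the Summary, schema and datasheet, including how the first 5-15 minutes in 4.2 relate to the 10-minute familiarization in the Summary.

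**Sections 7.1-7.4.** Name one matched score, of the sponsor's choice, as primary for the 3.5-point difference and SD of 10, the paired test or mixed model, and the Table 1 boundaries. Make the other score secondary. Do this before the n=52 look; the change to 4.2 should come as early as possible, because missed observations cannot be recovered.

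**Cost.** Protocol wording, and a few more minutes of scoring by the tablet observer at each non-VR visit. N=77 is unchanged.

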4.3 Follow-up Procedures

We will examine the CCBD schedule for the second opportunity to include each subject and complete the study in the other study arm (VR-distraction or Non-VR distraction). Surveys and Assessments will be filled out twice: once without the use of VR (control group) and the second time with the use of VR (study group).

Randomized Pilot Crossover Study Comparing Virtual Reality (VR) and Non-VR Distraction for Decreasing Preoperative/Procedural Anxiety as a Function of the modified Yale Preoperative Anxiety Scale (mYPAS)

Data collected will be compared and analyzed for statistically significant difference in anxiety scores with mYPAS. Parents' questionnaires will also be scored and evaluated for subjective improvement in parental assessment of preoperative anxiety.

All the study forms and questionnaires will be identified with the unique study ID number assigned in the study system with no other identifying data. There are no additional procedures outside the standard of care participants would normally receive. There will be no additional costs to subjects for participating in this study.

